Female patients of childbearing potential will undergo a pregnancy test, and be excluded from the study if positive.

2. Inability (e.g. dysphagia) to or unwilling to swallow capsules.
3. Active antibiotic-resistant bacteria (ARB) or gastrointestinal infection at time of enrollment.
4. Patient received antibiotics or probiotics in the last 48 hours. Patients will be eligible to enroll if antibiotic therapy is discontinued for at minimum 48 hours prior to randomization. Does not include antibiotics used for prophylaxis or topical antibiotics.
5. Requires continued antibiotic use or anticipates antibiotic use in the upcoming 4 weeks. Does not include antibiotics used for prophylaxis or topical antibiotics.
6. Unwilling to withhold probiotics for a minimum of 48 hours prior to providing a screening stool sample.
7. Known or suspected toxic megacolon and/or known small bowel ileus.
8. Major gastrointestinal surgery (e.g. significant bowel resection) within 3 months before enrollment. This does not include appendectomy or cholecystectomy.
9. History of total colectomy or bariatric surgery.
10. Admitted to or expected to an intensive care unit for medical reasons (not just boarding). Patients residing in a nursing home, long-term care facility or rehabilitation center may be enrolled.
11. Concurrent intensive induction chemotherapy, radiation therapy or biological treatment for active malignancy. Patients on maintenance chemotherapy may be enrolled only after consultation with medical monitor.
12. Unable or unwilling to comply with protocol requirements.
13. Expected life expectancy < 6 months
14. Previous FMT or microbiome-based products at any time excluding this study.
15. Patients with a history of severe anaphylactic or anaphylactoid food allergy.

16. Solid organ transplant recipients \leq 90 days post-transplant or on active treatment for rejection.
17. Neutropenia (\leq 500 neutrophils/mL) or other severe immunosuppression. Anti-TNF will be permitted. Patients on monoclonal antibodies to B and T cells, glucocorticoids, antimetabolites (azathioprine, 6-mercaptopurine, methotrexate), calcineurin inhibitors (tacrolimus, cyclosporine) and mycophenolate mofetil may be enrolled only after consultation with the medical monitor.
18. If at risk for CMV/EBV associated disease (at investigator's discretion, e.g. immunocompromised), negative IgG testing for cytomegalovirus (CMV) or Epstein Barr Virus (EBV).

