5. Males must agree to avoid impregnation of women during and for four weeks after completing study treatment. through use of an acceptable method of contraception.

Note: §Includes, but is not limited to, barrier with additional spermicidal foam or jelly, intrauterine device, hormonal contraception (started at least 30 days prior to study enrollment), intercourse with men who underwent vasectomy.

C.5.2 Participant Exclusion Criteria

Participants will not be able to participate if they meet any of the following exclusion criteria:

1. Female patient who are pregnant, lactating or planning on becoming pregnant during study. Female patients of childbearing potential will undergo a pregnancy test, and be excluded from the study if positive.
2. Inability (e.g. dysphagia) to or unwilling to swallow capsules.

3. Active antibiotic-resistant bacteria (ARB) or gastrointestinal infection at time of enrollment.
4. Patient received antibiotics in the last 48 hours. Patients will be eligible to enroll if antibiotic therapy is discontinued for at minimum 48 hours prior to randomization. Does not include antibiotics used for prophylaxis or topical antibiotics.
5. Requires continued antibiotic use or anticipates antibiotic use in the upcoming 4 weeks. Does not include antibiotics used for prophylaxis or topical antibiotics.
6. Unwilling to withhold probiotics for a minimum of 48 hours prior to providing a screening stool sample.
7. Known or suspected toxic megacolon and/or known small bowel ileus.
8. Major gastrointestinal surgery (e.g. significant bowel resection) within 3 months before enrollment. This does not include appendectomy or cholecystectomy.
9. History of total colectomy or bariatric surgery.
10. Admitted to or expected to an intensive care unit for medical reasons (not just boarding). Patients residing in a nursing home, long-term care facility or rehabilitation center may be enrolled.
11. Concurrent intensive induction chemotherapy, radiation therapy or biological treatment for active malignancy. Patients on maintenance chemotherapy may be enrolled only after consultation with medical monitor.
12. Unable or unwilling to comply with protocol requirements.
13. Expected life expectancy < 6 months
14. Previous FMT or microbiome-based products at any time excluding this study.
15. Patients with a history of severe anaphylactic or anaphylactoid food allergy.
16. Solid organ transplant recipients ≤ 90 days post-transplant or on active treatment for rejection.

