17. Neutropenia (≤ 500 neutrophils/mL) or other severe immunosuppression. Anti-TNF will be permitted. Patients on monoclonal antibodies to B and T cells, glucocorticoids, antimetabolites (azathioprine, 6-mercaptopurine, methotrexate), calcineurin inhibitors (tacrolimus, cyclosporine) and mycophenolate mofetil may be enrolled only after consultation with the medical monitor.
18. If at risk for CMV/EBV associated disease (e.g immunocompromised), negative IgG testing for cytomegalovirus (CMV) or Epstein Barr Virus (EBV).
19. A condition that would jeopardize the safety or rights of the subject, would make it unlikely for the participant to complete the study, or would confound the results of the study.

C.5.3 Treatment Assignment Procedures

C.5.3.1 Randomization Procedures

Participants who fulfill the criteria for randomization, will be randomized on a 1:1 basis with a with random permuted blocks (size of 2 or 4) to receive FMP-402 or placebo. Participant's randomization will be carried out by a bioinformatician based at OpenBiome using random number generation software to create a randomization schedule.

C.5.3.2 Masking Procedures

This is a double blinded placebo controlled trial where both the participant and treating physicians will be blinded. FMP-402 or placebo will be dispensed by OpenBiome thereby maintaining blinding of study clinician. Packaging will be identical and consist of the same saline and glycerol buffer used in FMT processing without the addition of microbiota.

Under normal circumstances, the blind should not be broken. The blind should be broken only if specific emergency treatment would be dictated by providing the treatment the participant was receiving. In such cases, the site PI must contact the Medical Monitor to request that the blind be broken. For participants who require unblinding, this information will be captured in the case report form (CRF).

The randomization schedule will be maintained by OpenBiome. Study participants or legal guardians will remain blinded and not be provided any information until all participants have completed the trial.

C.5.3.3 Reasons for Withdrawal

A participant may withdraw from the study at any time for any reason, without any consequence. A participant may be withdrawn from the study by the site PI for the following reasons:

Adverse event that may make it no longer in the best interest of the subject to continue participation in the study

Participant choice (withdrawal of consent)

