Placebo capsules will be identical in appearance to FMP-402 capsules but will not have human feces, [REDACTED]

[REDACTED] processed as described in OpenBiome's BBMF #

17300 [REDACTED]

C.6.3. Product Storage and Stability

Produced material will be stored at -80°C and each unit will have a date of production printed on it for tracking purposes. Studies have been conducted to ensure long-term bacterial viability following the freezing process based on studies conducted by Hamilton et. al and Youngster et. al.^{40,41} Local site storage at -20°C will be permitted for up to 6 months.

FMP-402 is currently undergoing stability testing, therefore expiration dates will not be provided with each unit. Instead, storage requirements will be provided via correspondence from the manufacturing company, Finch Therapeutics. Results from ongoing stability testing will be provided by Finch Therapeutics to partner sites, through OpenBiome, on an anticipated monthly basis. If units are determined to be unstable, Finch Therapeutics will communicate with OpenBiome to destroy the relevant units.

C.6.4 Dosage, Preparation and Administration of Study Intervention/Investigational Product

Participants will receive a single dose of 30 FMP-402 or placebo capsules. The dosing rationale is driven by the successful VRE decolonization for 2 patients with recurrent CDI and co-colonization of VRE following a single dose of 30 OpenBiome FMT capsules. Participants will undergo capsule administration by the following process:

- Document Review: Confirmation/review of exclusion criteria/contraindications as previously described.
- Safety Capsules: Direct observed capsule test, where participants will ingest one inert, size 00 ‘safety’ capsule under direct supervision of the study physician/nurse.
- Dietary instructions: Patients should maintain a clear liquid diet the day of administration and should fast (NPO) for a minimum of 2 hours prior to administration
- Capsule administration:
 - a. Patient should ingest 30 capsules (FMP-402 or placebo) under the direct observation of a physician/nurse. Patients may have water during capsule administration.
 - b. Patient should ingest capsules after extraction from freezer, and no longer than 60 minutes after removal.
 - c. Patients should remain fasting (NPO) for 1 hour following ingestion but may then return to a full diet.

C.6.5 Accountability Procedures for the Study Intervention/Investigational Product

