9. NSAID
10. Acid-blockers
11. Anticoagulants
12. Opioids
13. Iron supplementation
14. Anti-TNF will be permitted. Patients on monoclonal antibodies to B and T cells, glucocorticoids, antimetabolites (azathioprine, 6-mercaptopurine, methotrexate), calcineurin inhibitors (tacrolimus, cyclosporine) and mycophenolate mofetil may be enrolled only after consultation with the medical monitor.

Participants will be eligible to enroll 48 hours after their last dose of antibiotics; however, topical and prophylactic antibiotics will be permitted. Participants are also eligible to enroll 48 hours after their last dose of probiotics.

C.7. STUDY SCHEDULE

A schematic representation of the study schedule can be found in Appendix 17.2.

C.7.1 Screening (Visit 1)

Screening will take place with both passive and active systems. From a passive system perspective, VRE positive stool samples will be identified by each sites

laboratory and compiled lists of candidate participants distributed for study evaluation. Patients previously marked VRE positive in the medical records will also be approached for study evaluation. From an active system perspective, individuals at high-risk for VRE colonization including but not limited to those discharged from ICU to ward after a greater than 3 days stay, undergoing chronic dialysis, have an oncology or stable organ transplant history will be approached for consent to screen for VRE.⁴² Awareness about the study will be raised by standard, approved recruitment techniques and discussions with key stakeholders including clinical microbiology, infectious diseases and laboratory medicine teams. Past VRE positive patients in the health system may also be eligible to participate, provided that they fulfill eligibility criteria, and will be contacted by the research staff and invited to participate via an invitation letter/telephone follow-up call (UW) or with an invitation via telephone call (IU).

If patients are interested in participating in the study, and have been discharged from the hospital, stool samples can be submitted for screening for VRE colonization with a waiver of consent documentation. Patients being seen in any ambulatory setting in the health system are eligible if they are known to be VRE or at risk of having VRE.

If on probiotics at time of screening then patients will be advised to withhold probiotics for 48 hours prior to providing a sample.

C.7.2 Enrollment and Intervention Administration (Visit 2)

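### The only numeric neutropenia limit in exclusion criterion 17 is written per mL, which is 0.5 cells per microlitre, so the number does not do the job of the word it defines

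*Combined protocol and SAP*

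**What the plan says.** Criterion 17 of C.5.2 excludes "Neutropenia (≤ 500 neutrophils/mL) or other severe immunosuppression". The Protocol Summary, under Participant Exclusion Criteria, has the same number and unit: "500 neutrophils/mL) or other severe immunosuppression". Both copies go on to permit anti-TNF treatment and to allow a list of other immunosuppressants after consultation with the medical monitor. No other section gives a neutrophil count, a unit for one, or a definition of neutropenia.

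These provisions bear on how much the number matters:

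- **Product.** C.6.3 treats survival of the bacteria as a product property: "Studies have been conducted to ensure long-term bacterial viability following the freezing process".
- **Recruitment.** C.7.1 lists groups to be approached actively, among them patients who "have an oncology or stable organ transplant history will be approached for consent to screen for VRE".
- **Criterion 11.** It excludes concurrent intensive induction chemotherapy, radiation or biological treatment for active malignancy, but adds: "Patients on maintenance chemotherapy may be enrolled only after consultation with medical monitor".
- **Criterion 16.** It excludes solid organ transplant recipients within 90 days of transplant or under treatment for rejection.
- **Criterion 19 (C.5.2).** It excludes, among other things, "A condition that would jeopardize the safety or rights of the subject".

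**The concern.** The criterion attaches a number to the word neutropenia, and the two do not fit. At 500 per mL the limit describes a patient with essentially no circulating neutrophils. A patient with a very low but measurable count falls outside it.

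This is an operative safety limit for a product containing viable bacteria. The trial seeks out oncology and transplant patients and can admit patients on maintenance chemotherapy or immunosuppressants, so low counts are foreseeable. Immunocompromised patients are also a planned subgroup for a secondary efficacy outcome (C.3.2.1), and this boundary helps decide who can be in it.

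There is a conduct question too. C.14.6 counts any noncompliance with the protocol as a deviation. If a patient with a low count is enrolled, a monitor reading the number literally finds no breach of the numeric limit, while one reading the word neutropenia may find one. Neither the enrollment data points in C.7.2.1 nor the visit table in C.17.2 lists a blood count, so the text does not show how the comparison would be made.

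**Working it through.** The limit is stated without derivation, so there is no figure to reproduce. The check is a unit conversion, followed by a look at what else could exclude the same patients.

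**Inputs.** Limit: at most 500 neutrophils/mL (criterion 17, both copies). Conversions: 1 mL = 1,000 microlitres; 1 L = 1,000 mL.

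**Step 1, the limit in other units.**
- Per microlitre: 500 / 1,000 = 0.5.
- Per litre: 500 x 1,000 = 500,000, which is 0.0005 x 10^9/L.

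**Step 2, an illustrative patient.** Take 100 neutrophils per microlitre, a value chosen only for illustration.
- Per mL: 100 x 1,000 = 100,000.
- Against the limit: 100,000 / 500 = 200.

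This patient is 200 times above the written limit and does not meet it.

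**Step 3, the size of the unit question.** The same numeral read per microlitre would be 500 x 1,000 = 500,000 per mL, or 0.5 x 10^9/L. The ratio is 500,000 / 500 = 1,000. This shows scale only and does not imply that it is the intended limit.

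**Step 4, other routes to exclusion.**
- Second limb of criterion 17: covers other severe immunosuppression; undefined, no count, rests on judgement.
- Medical monitor consultation (criteria 11 and 17): applies to maintenance chemotherapy and the named drugs; no count, rests on judgement.
- Criterion 11: excludes specific cancer treatments; no count.
- Criterion 16: excludes specific transplant situations; no count.
- Criterion 19: a general safety clause; no count, rests on judgement.

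These routes may exclude or screen some patients with low counts. None restates or corrects the number.

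**The case against.** The strongest objection is that this may be a reading fault and not an error in the plan. The machine-read text contains at least one apparent Greek-letter substitution: in C.2.2 a gamma seems to have become a Latin y. A font-mapping fault could likewise turn a micro sign into an m. Because the criterion is nearly identical in the two places, a systematic fault would affect both, so their agreement is limited evidence. Against this, the inequality sign was rendered differently in the two copies, yet both read mL. The y for gamma is a look-alike, and a look-alike for the micro sign would be u. The possibility stands, unproven either way, and checking the source settles it.

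A second objection is that other provisions address the same patients. That stands in part. A reader might infer from the conversion that the safety exclusion has no effect, or that almost no neutropenic patient would be kept out. The documents do not support either inference: criterion 17 has a second limb, criteria 11 and 16 exclude named oncology and transplant situations, criterion 19 is a general safety clause, and several drug groups need consultation first. These provisions do not, however, repair the number.

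A third objection is that clinicians will know what was meant and that nothing suggests either site would apply 0.5 per microlitre. That is plausible, and divergence between the two sites is a possibility, not a finding. But eligibility would then rest on a correction that is not written down.

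**Conclusion.** The point holds for the numeric limit only. As the text reads, the one neutrophil count in the protocol equals 0.5 per microlitre, in effect zero, and does not serve the word it defines. The conversion is exact, and the unit question is worth a factor of 1,000. Other provisions may still exclude some of the patients concerned, so the exclusion as a whole is weakened, not void. How many patients are affected cannot be derived, because the documents give no distribution of counts.

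The conclusion rests on two assumptions. The first is that /mL is what the source prints. A reader might take an authoring error as established, but the machine-read text cannot show that. The second is that 0.5 per microlitre is effectively zero, which relies on the ordinary scale of blood counts and not on anything in the documents. The point has no bearing on the sample size, the primary endpoint or the analysis.

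**What to change.** 1. Check the unit in both copies of criterion 17 against the source document. If it is a micro sign misread as m, the matter closes at no cost.
2. If /mL is printed, the sponsor should reconcile the number and unit with its intended definition of neutropenia. It should then state the result identically in the Protocol Summary and C.5.2, in the unit in which the site laboratories report the neutrophil count. The threshold is for the sponsor to confirm.

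The cost is a short correction in two places, by amendment or clarification letter.

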Protocol violation/non-compliance

Pregnancy

Lost to follow up

Other (must be noted)

C.5.3.4 Handling Withdrawals

The primary reason for withdrawal from the study will be recorded on the Study Status CRF page. Participants will be encouraged to complete the Early Termination Visit. The Early Termination Visit procedures are listed. Although participants are free to withdraw at any time, participants will be encouraged to remain in the study for follow-up safety evaluation. Every attempt should be made to follow all AEs and SAEs ongoing at the time of early withdrawal to resolution or until stabilized. If possible, a final stool sample will be collected at the Early Termination Visit. Intention-to-treat analysis will be utilized according to best practices in clinical trials. Attempts will be made to complete safety follow-up for all subjects who have received the study product, including those who have discontinued participation in other study procedures, for the duration of the planned follow-up period.

Participants who are withdrawn from the study after randomization but before intervention or placebo will be replaced. Possible reasons for participant withdrawal after randomization include but are not limited to:

- Participants who are started on a new course of antibiotics after randomization and before intervention/placebo
- Unrelated participant death

C.5.3.5 Termination of Study

In the unlikely event that significant safety concerns arise, the PIs can terminate or halt the study pending review by the DSMB. In addition, this study may be halted early based on the DSMB charter or FDA recommendations.

C.6. STUDY INTERVENTION/INVESTIGATIONAL PRODUCT

C.6.1 Study Product Description

FMP-402 is encapsulated fecal microbiota sourced from human-derived microbes. The human source generating the fecal microbes has been extensively screened for infectious pathogens and microbiome mediated diseases using a standardized process (found in OpenBiome's BBMF # 15543, Section F). Additionally, the capsule delivery vehicle enables targeted deposition of the investigational active pharmaceutical ingredient into the colon.

C.6.2 Formulation

C.6.2.1 Encapsulated fecal microbiota preparation (formulation FMP-402)

This formulation is encapsulated fecal microbiota sourced from human-derived microbes generated by healthy, screened donors, as described in OpenBiome's [REDACTED]

BBMF # 17300

C.6.2.2 Placebo

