For non-serious adverse reactions (definitely related, possibly related, not related) the site PI will complete a report and submit it to the medical monitor and lead PI. All non-serious adverse reactions will be reviewed by the DSMB every 6 months or *ad hoc* depending on the clinical case at the discretion of the site PI, study medical monitor and lead PI.

In accordance with safety requirements, the site PI will inform the local IRB and lead PI and will make sure that the involved persons will obtain adequate information. The following instructions must be heeded:

- In the case of an intolerable SAE, the study patient must, at the decision of the site PI, be withdrawn from further treatment/placebo, and symptomatic treatment must be administered. The participant may opt to voluntarily providing sample for duration of study.
- The measures taken must be recorded on the CRF.
- In accordance with local legislation, the site PI will submit copies of the final SAE-report to the Regulatory Authorities concerned, if necessary.

C.8.8 Follow-up of Participants after Adverse Events

AEs will be followed until resolution or stability even if this extends beyond the study-reporting period. Resolution of an AE is defined as the return to pretreatment status or stabilization of the condition with the expectation that it will remain chronic.

Follow-up procedures, evaluations, and outcomes will be recorded on the participant's case report forms.

C.8.9. Halting Rules

C.8.9.1 Study Halting Rules

Enrollment and administration of study intervention will be suspended pending a safety review by the DSMB to determine whether the study will be terminated or re-initiated in the following situations:

Three or more of the randomized participants in a study treatment group have a Grade 3 AE of the same organ system deemed related to the study intervention.

Any serious adverse event of an enrolled participant related to the study intervention including transmission of a pathogen from donor to recipient. An overall pattern of symptomatic, clinical, or laboratory events that the Medical Monitor considers related to study product and that may appear minor in terms of individual events, but that may collectively represent a serious potential concern for safety.

CBER will be notified of any study halt that occurs as a result of any of the above halting criteria.

C.8.9.2 Individual's Halting Rules

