Participants who meet any of the following criteria must be assessed by the site PI to determine if it is in the participant's best interest to stop the study product(s):

- Participant choice (withdrawal of consent).
- Participant's non-compliance.
- Development of a significant medical condition and/or participation in the study is no longer in the best interest of the participant.

All attempts will be made to complete safety follow-up for participants who received the study product, but discontinued participation in other study procedures, for the duration of the planned follow-up period.

C.8.10 Safety Oversight

C.8.10.1 Data and Safety Monitoring Board (DSMB)

Safety oversight will be under the direction of a DSMB. The DSMB is an independent group of experts who will advise the study PIs. The primary responsibilities of the DSMB are to 1) periodically review and evaluate the accumulated study data for participant safety, study conduct and progress, and, when appropriate, efficacy, and 2) make recommendations to the continuation, modification, or termination of the trial. The DSMB will be composed of at least 3 voting members. The membership will include a chairperson who has prior DSMB experience. One member will be an experienced gastroenterologist and one member will be an experienced infectious disease specialist. All DSMB members will be separate and independent of study personnel participating in this trial and should not have scientific, financial or other conflict of interest related to the trial. Procedures for DSMB data reviews will be defined in the DSMB Charter that will include DSMB membership, responsibilities, and the scope and frequency of data reviews. The DSMB will have access to unblinded treatment assignments during the closed session of their meetings. The study should be reviewed by the DSMB at least bi-annually. The DSMB may conduct a safety interim analysis after 50% of patients have enrolled in the treatment arm.

C.9. CLINICAL MONITORING

C.9.1 Site Monitoring Plan

Site monitoring is conducted to ensure that the human participant protection, study and laboratory procedures, study intervention administration, and data collection processes are of high quality. The lead PI (or delegate) will conduct a site-monitoring visit(s) as detailed in a monitoring plan. The PIs will permit authorized representatives of CDC, regulatory agency and/or an auditing body to inspect facilities and records relevant to this study, if needed.

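### Withdrawal rules do not separate stopping product from leaving the study, so a dosed participant withdrawn before Day 10 may have no primary culture

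*Combined protocol and SAP*

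**What the plan says.** **Permission to withdraw (C.5.3.3).** "A participant may be withdrawn from the study by the site PI for the following reasons". The list includes "Adverse event that may make it no longer in the best interest of the subject to continue participation in the study", "Protocol violation/non-compliance", pregnancy, loss to follow-up and other. The section does not say whether it applies before dosing, after dosing or both.

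**Product (C.6.4).** "Participants will receive a single dose of 30 FMP-402 or placebo capsules". Under C.6.6, capsules left over may be offered only on the same day.

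**Primary endpoint (C.3.2.1).** Absence of VRE on stool culture at Day 10 (±3 days) after randomization.

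**What continues after withdrawal.**
- C.5.3.4: "participants will be encouraged to remain in the study for follow-up safety evaluation". On stool: "If possible, a final stool sample will be collected at the Early Termination Visit". The same section invokes intention-to-treat and replaces only participants withdrawn before dosing.
- C.7.4 lists an early termination stool for 16S sequencing and ARB PCR, and asks permission for passive records follow-up where visits or stool are not feasible.
- C.7.4 and C.8.9.2 both promise attempts to "complete safety follow-up for participants who received the study product, but discontinued participation in other study procedures".
- C.8.7, on an intolerable SAE leading to withdrawal from further treatment: "The participant may opt to voluntarily providing sample for duration of study".

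**Analysis (C.10.1, C.10.2).** The design assumes 85% versus 40%, power 0.9, two-sided alpha 0.05 and 15% drop-out, giving n=46. No rule is given for a missing Day 10 result.

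**The concern.** In a multi-dose trial, an investigator who withdraws a participant usually stops exposure. Here exposure is complete on Day 0, so once a participant has been dosed, withdrawal from the study affects only what is collected afterwards. The text that follows protects safety data and leaves the efficacy sample to chance.

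The primary result depends on one stool taken in a seven-day window (Days 7 to 13). A participant withdrawn on, say, Day 4 may give an early termination stool, but it would fall outside the window, and culture is not among the tests listed for it. (Visit 4 in C.7.3.2 omits culture too.) The intention-to-treat statement cannot be honoured for a culture that was never taken, and C.10.2 does not say how such a participant would be counted.

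Some of the listed reasons, such as an adverse event after the capsules, could be related to arm or to outcome even when everyone is blinded. With 23 per arm, a handful of such losses matters.

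**Working it through.** **1. The plan's own figure.** Inputs from C.10.1: p1=0.85, p2=0.40, power 0.9, alpha 0.05 (two-sided per C.10.2), drop-out 15%.

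Unpooled normal approximation: n = (1.960 + 1.282)² × (0.85×0.15 + 0.40×0.60) / 0.45² = 19.07, so 20 per arm.
- 20 × 1.15 = 23 per arm, 46 in total, which is the stated figure.
- Dividing by 0.85 instead gives 24 per arm, 48 in total.
- The pooled two-sided formula needs 23 per arm evaluable before any drop-out, so there is little slack.

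**2. Power with and without the missing cultures (missing at random).**

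| Evaluable per arm | Pooled normal | Fisher exact |
|---|---|---|
| 23 | 0.911 | 0.853 |
| 20 | 0.866 | 0.797 |
| 19 | 0.847 | 0.783 |

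**3. Upper illustration: the whole planned drop-out is missing.** 46 × 0.15 = 6.9, taken as 7 (3 on FMP-402, 4 on placebo). The observed counts are assumed, chosen near the design rates. Fisher's test is also an assumption, since C.10.2 names no test.
- Observed: 17/20 − 8/19 = 0.850 − 0.421 = 0.429 (p=0.008).
- Lowest full-set value (lost FMP-402 participants all still colonized, lost placebo participants all cleared): 17/23 − 12/23 = 5/23 = 0.217 (p=0.22).
- Highest (the reverse): 20/23 − 8/23 = 12/23 = 0.522.
- Each culture kept narrows this range by 1/23 = 4.3 points.

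**4. Small illustration: one loss per arm.** Assumed observed 19/22 versus 9/22.
- Lowest: 19/23 − 10/23 = 9/23 = 0.391 (p=0.013).
- Highest: 20/23 − 9/23 = 11/23 = 0.478 (p=0.002).
- The conclusion is the same at both ends.

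**5. The sections side by side.**

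| Section | Withdrawn from what | Efficacy sample afterwards |
|---|---|---|
| C.5.3.3 / C.5.3.4 | the study | one stool, if possible, on no fixed day |
| C.7.4 | early termination | stool for 16S and ARB PCR; records if stool is not feasible |
| C.8.7 | further treatment or placebo | may continue for the study's duration, voluntarily |
| C.8.9.2 | study product(s) | none mentioned; safety follow-up only |

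None of the four requires the Day 10 culture from a dosed participant. C.8.7 and C.8.9.2 speak of stopping product when none remains to be given.

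**The case against.** The plan is not indifferent to follow-up. Participants are encouraged to attend an early termination visit, stool is collected there by default with records as the fallback, safety follow-up is attempted for everyone dosed, and intention-to-treat is named. The C.5.3.3 list also serves withdrawals between randomization and dosing, where ending participation makes sense. The adverse-event reason is tied to the participant's best interest. All of this stands, but none of it obtains a culture inside Days 7 to 13.

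Several stronger readings are tempting, and the documents do not support them.
- *That such a withdrawal can only cost the primary culture.* A withdrawal after the Day 10 visit costs no primary result, and an early termination stool may happen to fall in the window.
- *That the loss is selective.* Participants and treating physicians are blinded, and no withdrawal rates by arm or reason are given. Antibiotics started after dosing are not a listed withdrawal reason, and C.7.5 records the infection and attempts a stool. With a negative test required on the day of dosing and no later test scheduled, pregnancy is a negligible route to a lost Day 10 result.
- *That a participant with a worse event keeps the endpoint while one with a milder event loses it.* This reads a prohibition into silence: C.8.7 mentions continued sampling, but no section forbids it for others.
- *That the 22-to-52-point range measures this defect.* It applies all-cause drop-out, of which investigator-initiated withdrawal is an unknown part.

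**Conclusion.** The point holds as a gap in data collection. For a dosed participant withdrawn before Day 10, the plan secures safety follow-up but not the primary culture, and its withdrawal sections do not fit a single-dose product or one another.

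The size depends on how many such withdrawals occur, which the documents do not say. If all 15% of cultures were missing, for whatever reason, the assumed 43-point result could lie between 22 and 52 points and significance would depend on cultures nobody took. With one loss per arm, the conclusion survives. Bias is possible but not shown.

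A reader might also infer that the investigator's power to withdraw a participant for an adverse event or pregnancy should be removed. That does not follow: the discretion protects participants and is for the sponsor to settle, and the culture can be secured without touching it. It is a worthwhile, inexpensive improvement, not a fatal flaw.

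**What to change.** - **C.5.3.4, C.7.4 and C.8.9.2:** state that any dosed participant who is withdrawn or stops visits, and who has not withdrawn consent to sampling, is still asked for the scheduled Day 10 (±3) and Week 4 stool. Use the mail or drop-off route in C.7.6, which is now written for telephone visits. State that the Day 10 sample is cultured for VRE, and that an early termination stool before Day 7 does not replace it.
- **C.5.3.3:** separate stopping product from ending follow-up. State that a protocol violation or non-compliance after dosing is recorded as a deviation and does not by itself end data collection.
- **C.5.3.3, C.8.7 and C.8.9.2:** reconcile the references to further treatment and study product(s) with the single dose, leaving the investigator's participant-protection discretion to the sponsor.

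The cost is wording in a few sections and a few more mailed kits and calls, with no new visits. The documents do not say whether a mailed sample is acceptable for culture, so the laboratory should confirm this.
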